6.11 Subject Replacement Strategy

Additional subjects may be enrolled to ensure that the required number of evaluable subjects in each cohort is achieved. A subject that discontinues the trial for progressive disease or a drug-related AE will not be replaced and will be counted in the evaluable population of subjects for the respective cohort. Patients will be considered evaluable if they have received any treatment with pembrolizumab.

6.12 Clinical Criteria for Early Trial Termination

Early trial termination will be the result of the criteria specified below:

1. Quality or quantity of data recording is inaccurate or incomplete
2. Poor adherence to protocol and regulatory requirements
3. Incidence or severity of adverse drug reaction in this or other studies indicates a potential health hazard to subjects
4. Plans to modify the development of the study drug

In the event of Merck decision to no longer supply study drug, ample notification will be provided so that appropriate adjustments to subject treatment can be made.

6.13 Correlative Analysis and Methodology

6.13.1 Archival tissue

Previously obtained or fresh frozen tissue is acceptable. For FFPE tissue 14 to 20, 5 micron slides are requested. Slides will be stored in the HTRC pathology core at the University of Chicago. If possible additional slides will be requested using OncoPlexDx compatible slides (see OncoPlex Dx general instructions on their website for further details).

Predefined Analyses include:

- 1) Staining for PD-L1 by IHC using the 22C3 antibody via a commercial provider in a CLIA laboratory
- 2) PD-L1 and CD8 determination via OncoPlexDx in a CLIA environment
- 3) Multiplex staining (one or several slides) for multiple immune markers including IDO, PD-L1, CD8, FOXP3; additional staining may be performed for additional markers. Additional markers will be analyzed

6.13.2 Fresh tumor biopsies

If clinically indicated tissue from a biopsy will also be banked using the UCCCC# 9571 banking protocol. The following clinical situations should be considered for obtaining additional tissue for banking purposes and biomarker analysis as outlined below:

1. Baseline biopsy e.g. indicated diagnostically
2. Possible tumor flare should be considered for biopsy to assess immune cell infiltration
3. Tumor progression – especially after prior benefit from therapy to rule out pseudoprogression and identify possible mechanisms of resistance using the methodologies described in this section.
4. Other clinically appropriate scenarios – e.g. assessment of residual tumor may be considered for biopsy.

6.13.3 TCR sequencing

TCR sequencing analysis will be performed using the Adaptive commercial platform or collaborative work at the University of Chicago in [name] lab. Fresh Frozen tumor tissue will be used preferentially (but FFPE compliant technology is in testing and samples will be collected as a backup on all patients). Specific information for sample preparation is available via the Adaptive Website (Adaptive Biotechnologies, Seattle WA <http://www.adaptivebiotech.com/technology/>).

6.13.4 Nanostring Analysis

From 3-5 FFPE slides RNA will be extracted using the Qiagen RNA/DNA FFPE kit and protocol. A Nanostring probeset including ca 20-150 immune and other marker related probes will be used using the Nanostring (Seattle) standard ordering and analysis process. The

Nanostring nCounter available in the [name] lab at the University of Chicago will be used. Alternatively FFPE based RNAseq libraries may be constructed using the Illumina FFPE RNA access protocol. The [name] lab is experienced with both the Nanostring and FFPE RNAseq process and additional details are available on request. These are exploratory analyses and laboratory protocols are constantly updated.

6.13.5 Tumor DNA analysis

Exome or more focused panel sequencing (e.g. Foundation One) will be performed on the majority of tumor samples for an exploratory analysis of correlation of genetic aberrations, immune phenotype and tumor response.

6.13.6 Germline DNA analysis

Blood will be obtained from all patients enrolled in the study for pharmacogenomic evaluation. Investigation of the relevant polymorphisms will take place in germline DNA extracted from peripheral whole blood (10 ml) collected in plastic EDTA (lavender top) vacutainers (BD catalog#366643). Blood samples after necessary processing in the CTCRC (pathology) should be stored at -80°C. Samples should be labeled with protocol number, patient initials, patient registration number, and the date and time of draw.

DNA extraction for genotyping will be performed according to commercially available DNA isolation kits, such as Puregene (Gentra Systems, Inc., Minneapolis, MN). Samples ideally should be collected prior to initiation of therapy; however, sample collections missed at the initiation of therapy still **can be collected at any time**, as genotype is not expected to change. Genotyping for the selected variants will be performed based on previously published methods for the variants of interest.

Specifically we aim to perform SNP genotyping to evaluate candidate SNPs related to immune function that were recently discovered (unpublished work). These SNP candidates will be first confirmed in the upcoming TCGA Mesothelioma cohort and their relation to immune markers. If successful this will be done for all patients on this study and correlated with the immune phenotype. This work will be done in collaboration with [name].

6.13.7 Flow Cytometric Analysis of Tumor Digests

Fresh tumor samples (as available) will be digested using a protocol for tumor digestion employing the Miltenyi GentleMACS system available in the HIM Core facility. Single cell

suspension will be stored for subsequent FACS/CyTOF multiplex immune marker analysis. Markers include those listed above as well as additional immune markers and are subject to change. Please refer to the detailed sample processing instruction/protocol which will be updated as appropriate and is therefore not included in the protocol as several parameters are still being optimized.

6.13.8 Flow Cytometric Analysis of PBMCs

Blood samples will be obtained at baseline and after cycle 3 using 2 (two) lavender- (EDTA) (or alternatively green- (sodium heparin)) tubes. Processing will occur in the HIM core facility following standard protocol for processing and storage of cell suspensions for later analysis by flow cytometry. Subsequent FACS/CyTOF multiplex immune marker analysis will be performed. Markers include those listed above as well as additional immune markers and are subject to change.

Section 6.13.9 Radiomics

The medical record numbers (MRN) for the 65 Mesothelioma patients receiving Pembrolizumab along with their pneumonitis status and scan date will be acquired and forwarded to HIRO. These data will be collected by HIRO and anonymized such that the research team will be provided with the patient scans without any patient-identifying information. HIRO will assign a case-identifying number to each patient in order to label all scans for each patient. Protected patient health information will be stored in password-protected files, and anonymization will comply with the Privacy Rule by removing all 18 private identifiers.

The anonymized patient scans acquired at various time points throughout treatment will be used by the research team to classify patients with and without immunotherapy-induced pneumonitis using quantitative texture features extracted from various regions throughout the images of the lungs. The lungs will be segmented, and two-dimensional regions of interest (ROI) will be randomly placed throughout the lungs in each axial slice of the baseline scan acquired prior to immunotherapy treatment. A maximum of ten 32x32-pixel ROIs will be placed in each axial slice of the baseline scans where no two ROIs overlap. Each ROI in the baseline scan will then be matched to the corresponding anatomical location in the followup scans using the vector map acquired from deformable registration. The pixel information from each ROI will be extracted and used to calculate various classifications of radiomics texture features, which describe the patterns in pixel intensity and spatial relationships of pixels within the ROIs. The change in feature values between time points will be calculated, and linear regression analysis will be used to determine if texture feature change is significantly related to pneumonitis status. Then, receiver operating characteristic (ROC) curve analysis will be used to evaluate the classification performance of regression modeling relating changes in texture features to pneumonitis status.

7.1 Study Flow Chart

Trial Period:	Screening Phase		Treatment Cycles *								End of Treatment	Post-Treatment		
Treatment Cycle/Title:	Pre-screening (Visit 1)	Main Study Screening (Visit 2)	1	2	3	4	To be repeated beyond 8 cycles **				Discontinuation (D/C)	Safety Follow-up(+/- 1 week)	Follow Up Visits (+/- 1 week)	Survival Follow-Up(+/- 2 weeks)
							5	6	7	8				
Scheduling Window (Days):		-28 to -1		± 3	± 3	± 3	± 3	± 3	± 3	± 3	At time of D/C	30 days post D/C	Every 8 weeks post D/C	Every 12 weeks
Administrative Procedures														
Informed Consent	X													
Inclusion/Exclusion Criteria	X	X												
Demographics and Medical History#	X	X												
Prior and Concomitant Medication Review	X	X	X	X	X	X	X	X	X	X	X			
Trial Treatment Administration			X	X	X	X	X	X	X	X				
Post-study anticancer therapy status											X			
Survival Status											X	X	X	X
Clinical Procedures/Assessments														
Review Adverse Events			X	X	X	X	X	X**	X	X**	X			
Full Physical Examination		X	X	X	X	X	X	X**	X	X**	X	X	X	
Vital Signs and Weight		X	X	X	X	X	X	X	X	X	X	X	X	
ECOG Performance Status		X	X	X	X	X	X	X**	X	X**	X	X	X	
Laboratory Procedures/Assessments: analysis performed by LOCAL laboratory														

Trial Period:	Screening Phase		Treatment Cycles *								End of Treatment	Post-Treatment		
			1	2	3	4	To be repeated beyond 8 cycles **				Discontinuation (D/C)	Safety Follow-up(+/- 1 week)	Follow Up Visits (+/- 1 week)	Survival Follow-Up(+/- 2 weeks)
Treatment Cycle/Title:	Pre-screening (Visit 1)	Main Study Screening (Visit 2)					5	6	7	8				
Scheduling Window (Days):		-28 to -1		± 3	± 3	± 3	± 3	± 3	± 3	± 3	At time of D/C	30 days post D/C	Every 8 weeks post D/C	Every 12 weeks
For Women of childbearing potential - Pregnancy Test – (continued) Urine or Serum β-HCG (also see Table 9, page 37)		X												
PT/INR and aPTT		X												
CBC with Differential		X	X	X	X	X	X	X	X	X	X	X	X	
Comprehensive Serum Chemistry Panel		X	X	X	X	X	X	X	X	X	X	X	X	
Urinalysis		X												
T3, FT4 and TSH		X					X				X			
Efficacy Measurements														
Tumor Imaging (every 9 weeks = 3 cycles)		X				X			X				X	
Tumor Biopsies/Archival Tissue Collection/Correlative Studies Blood														
Archival (or Newly Obtained) Tissue Collection (typically FFPE, ≥14 5micron slides to be collected, see 6.13.1 for additional details)		X												
Fresh Tumor Biopsies (optional) – to	X ¹													

Trial Period:	Screening Phase		Treatment Cycles [*]								End of Treatment	Post-Treatment		
Treatment Cycle/Title:	Pre-screening (Visit 1)	Main Study Screening (Visit 2)	1	2	3	4	To be repeated beyond 8 cycles ^{**}				Discontinuation (D/C)	Safety Follow-up(+/- 1 week)	Follow Up Visits (+/- 1 week)	Survival Follow-Up(+/- 2 weeks)
							5	6	7	8				
Scheduling Window (Days):		-28 to -1		± 3	± 3	± 3	± 3	± 3	± 3	± 3	At time of D/C	30 days post D/C	Every 8 weeks post D/C	Every 12 weeks
be obtained if biopsy is clinically justified														
Correlative Studies Blood Collection including a) germline DNA collection and b) Flow analysis (See Sections 6.13.6-7)		X ²			X ³									

Laboratory tests for screening or potentially a Second Treatment Course (see Section 8.1.5.2.1) should be performed within 14 days prior to the first dose of treatment. After Cycle 1, pre-dose laboratory procedures can be conducted up to 72 hours prior to dosing.

** Treatment cycle length = 21 days*

*** After cycle 8, as clinically appropriate ECOG performance status, physical exam, and adverse event recording interval may be increased to every other cycle (=every 6 weeks).*

This includes history of asbestos exposure (see Appendix 5—Mesothelioma Program Exposure History Form)

1. If clinically indicated tissue from a biopsy will also be banked using the UCCCC# 9571 banking protocol. The following clinical situations should be considered for obtaining additional tissue for banking purposes and biomarker analysis as outlined below (also see section 6.13.2:.

a) Baseline biopsy e.g. indicated diagnostically, b) Possible tumor flare should be considered for biopsy to assess immune cell infiltration, c) Tumor progression – especially after prior benefit from therapy to rule out pseudoprogression and identify possible mechanisms of resistance using the methodologies described in this section. d) Other clinically appropriate

Trial Period:	Screening Phase		Treatment Cycles *								End of Treatment	Post-Treatment		
Treatment Cycle/Title:	Pre-screening (Visit 1)	Main Study Screening (Visit 2)	1	2	3	4	To be repeated beyond 8 cycles **				Discontinuation (D/C)	Safety Follow-up(+/- 1 week)	Follow Up Visits (+/- 1 week)	Survival Follow-Up(+/- 2 weeks)
							5	6	7	8				
Scheduling Window (Days):		-28 to -1		± 3	± 3	± 3	± 3	± 3	± 3	± 3	At time of D/C	30 days post D/C	Every 8 weeks post D/C	Every 12 weeks
scenarios – e.g. assessment of residual tumor may be considered for biopsy.														
2. -- 2 + 2 Purple top tubes (see section 6.13.7-8), blood volume, processing etc will follow HTRC SOPs														
3. -- 2 Purple top tubes (see section 6.13.7-8), blood volume, processing etc will follow HTRC SOPs														

8.0 TRIAL PROCEDURES

8.1 Trial Procedures

The Trial Flow Chart - Section 7.0 summarizes the trial procedures to be performed at each visit. Individual trial procedures are described in detail below. It may be necessary to perform these procedures at unscheduled time points if deemed clinically necessary by the investigator.

Furthermore, additional evaluations/testing may be deemed necessary by the investigator and/or Merck for reasons related to subject safety. In some cases, such evaluation/testing may be potentially sensitive in nature (e.g., HIV, Hepatitis C, etc.), and thus local regulations may require that additional informed consent be obtained from the subject. In these cases, such evaluations/testing will be performed in accordance with those regulations.

8.1.1 Administrative Procedures

8.1.1.1 Informed Consent

The investigator must obtain documented consent from each potential subject prior to participating in a clinical trial.

8.1.1.1.1 General Informed Consent

Consent must be documented by the subject's dated signature or by the subject's legally acceptable representative's dated signature on a consent form along with the dated signature of the person conducting the consent discussion.

A copy of the signed and dated consent form should be given to the subject before participation in the trial.

The initial informed consent form, any subsequent revised written informed consent form and any written information provided to the subject must receive the IRB/ERC's approval/favorable opinion in advance of use. The subject or his/her legally acceptable representative should be informed in a timely manner if new information becomes available that may be relevant to the subject's willingness to continue participation in the trial. The communication of this information will be provided and documented via a revised consent form or addendum to the original consent form that captures the subject's dated signature or by the subject's legally acceptable representative's dated signature.

The informed consent will adhere to IRB/ERC requirements, applicable laws and regulations and Drug Manufacturer requirements.

8.1.1.2 Inclusion/Exclusion Criteria

All inclusion and exclusion criteria will be reviewed by the investigator or qualified designee to ensure that the subject qualifies for the trial.

8.1.1.3 Subject Identification Card

No Subject Identification Cards will be issued as part of this trial.

8.1.1.4 Medical History

A medical history will be obtained by the investigator or qualified designee. Medical history will include all active conditions, and any condition diagnosed within the prior 10 years that are considered to be clinically significant by the Investigator. Details regarding the disease for which the subject has enrolled in this study will be recorded separately and not listed as medical history.

8.1.1.5 Prior and Concomitant Medications Review

8.1.1.5.1 Prior Medications

The investigator or qualified designee will review prior medication use, including any protocol-specified washout requirement, and record prior medication taken by the subject within 28 days before starting the trial. Treatment for the disease for which the subject has enrolled in this study will be recorded separately and not listed as a prior medication.

8.1.1.5.2 Concomitant Medications

The investigator or qualified designee will record medication, if any, taken by the subject during the trial. All medications related to reportable SAEs and ECIs should be recorded as defined in Section 8.2.

8.1.1.6 Disease Details and Treatments

8.1.1.6.1 Disease Details

The investigator or qualified designee will obtain prior and current details regarding disease status.

8.1.1.6.2 Prior Treatment Details

The investigator or qualified designee will review all prior cancer treatments including systemic treatments, radiation and surgeries.

8.1.1.6.3 Subsequent Anti-Cancer Therapy Status

The investigator or qualified designee will review all new anti-neoplastic therapy initiated after the last dose of trial treatment. If a subject initiates a new anti-cancer therapy within 30 days after the last dose of trial treatment, the 30-day Safety Follow-up visit must occur before the first dose of the new therapy. Once new anti-cancer therapy has been initiated the subject will move into survival follow-up.

8.1.1.7 Assignment of Screening Number

All consented subjects will be given a unique screening number that will be used to identify the subject for all procedures that occur prior to treatment allocation and for Part B PD-L1 prescreening. Each subject will be assigned only one screening number. Screening numbers must not be re-used for different subjects. Any subject who is screened multiple times will retain the original screening number assigned at the initial screening visit.

8.1.1.8 Assignment of Randomization Number

No randomization will be performed and no randomization numbers will be performed. However patients in part B will be enrolled based on their PD-L1 expression level.

Once a screening number is assigned to a subject, it can never be re-assigned to another subject.

8.1.1.9 Trial Compliance (Medication/Diet/Activity/Other)

Interruptions from the protocol specified treatment plan for greater than 12 weeks between MK-3475/pembrolizumab doses due to toxicity require consultation between the investigator and the PI and written documentation of the collaborative decision on subject management. Administration of trial medication will be witnessed by the investigator and/or trial staff.

The total volume of trial treatment infused will be compared to the total volume prepared to determine compliance with each dose administered.

The instructions for preparing and administering pembrolizumab/MK-3475 will be provided in conjunction with the delivery of pembrolizumab/MK-3475.

8.1.2 Clinical Procedures/Assessments

8.1.2.1 Adverse Event (AE) Monitoring

The investigator or qualified designee will assess each subject to evaluate for potential new or worsening AEs as specified in the Trial Flow Chart and more frequently if clinically indicated. Adverse experiences will be graded and recorded throughout the study and during the follow-up period according to NCI CTCAE Version 4.0. Toxicities will be characterized in terms regarding seriousness, causality, toxicity grading, and action taken with regard to trial treatment.

All AEs of unknown etiology associated with pembrolizumab exposure should be evaluated to determine if it is possibly an event of clinical interest (ECI) of a potentially immunologic etiology (irAE). See the separate guidance document at the end of this protocol regarding the identification, evaluation and management of AEs of a potential immunological etiology.

Please refer to section 8.2 for detailed information regarding the assessment and recording of AEs.

8.1.2.2 Full Physical Exam

The investigator or qualified designee will perform a complete physical exam during the screening period. Clinically significant abnormal findings should be recorded as medical history. A full physical exam should be performed during screening,

8.1.2.3 Directed Physical Exam

For cycles that do not require a full physical exam per the Trial Flow Chart, the investigator or qualified designee will perform a directed physical exam as clinically indicated prior to trial treatment administration.

8.1.2.4 Vital Signs

The investigator or qualified designee will take vital signs at screening, prior to the administration of each dose of trial treatment and at treatment discontinuation as specified in the Trial Flow Chart (Section 7.0). Vital signs should include temperature, pulse, respiratory rate, weight and blood pressure. Height will be measured at screening only.

8.1.2.5 Eastern Cooperative Oncology Group (ECOG) Performance Scale

The investigator or qualified designee will assess ECOG status (see Section 13.1) at screening, prior to the administration of each dose of trial treatment and discontinuation of trial treatment as specified in the Trial Flow Chart. After Cycle 8 assessment of ECOG status will be performed every other cycle in conjunction with a physical exam (see Section 7).

8.1.2.6 Tumor Imaging and Assessment of Disease

CT scans or comparable transactional imaging will be obtained every 9 weeks (=3 treatment cycles).

Response will be assessed using mesothelioma response criteria/modified RECIST (Byrne 2004), as is common practice for mesothelioma trials, as RECIST criteria do not adequately capture treatment benefit.

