6.2.1.2 Dose Modification

Pembrolizumab will be withheld for drug-related Grade 4 hematologic toxicities, non-hematological toxicity \geq Grade 3 including laboratory abnormalities, and severe or life-threatening AEs as per Table 3 below.

Table 3: Dose modification guidelines for drug-related adverse events.

Toxicity	Grade	Hold Treatment (Y/N)	Timing for restarting treatment	Dose/Schedule for restarting treatment	Discontinue Subject (after consultation with Drug Manufacturer)
Hematological Toxicity	1, 2	No	N/A	N/A	N/A
	3* *Excluding Grade 3 neutropenia, anemia, and thrombocytopenia	Yes	Toxicity resolves to Grade 0-1 or baseline	May increase the dosing interval by 1 week	Toxicity does not resolve within 12 weeks of last infusion
	4	Yes	Toxicity resolves to Grade 0-1 or baseline	May increase the dosing interval by 1 week	Permanent discontinuation should be considered for any severe or life-threatening event
Non-hematological toxicity	1	No	N/A	N/A	N/A
	2	Consider withholding for persistent symptoms	Toxicity resolves to Grade 0-1 or baseline	Clinical AE resolves within 4 weeks: Same dose and schedule (reference Section 5.6.1.2 for recommendations regarding pneumonitis) Clinical AE does not resolve within 4 weeks: May increase the dosing interval	Toxicity does not resolve within 12 weeks of last infusion

Note:
Exception to be treated similar to grade 1 toxicity

- Grade 2 alopecia
- Grade 2 fatigue

Toxicity	Grade	Hold Treatment (Y/N)	Timing for restarting treatment	Dose/Schedule for restarting treatment	Discontinue Subject (after consultation with Drug Manufacturer)
For additional information regarding Adverse Events with a potential Immune-Etiology reference Section 5.6.1.1.				by 1 week for each occurrence	
	3, 4	Yes	Toxicity resolves to Grade 0-1 or baseline	May increase the dosing interval by 1 week for each occurrence	Toxicity does not resolve within 12 weeks of last infusion Permanent discontinuation should be considered for any severe or life-threatening event

In case toxicity does not resolve to Grade 0-1 within 12 weeks after last infusion, trial treatment should be discontinued after consultation with the PI. With PI agreement, subjects with a laboratory adverse event still at Grade 2 after 12 weeks may continue treatment in the trial only if asymptomatic and controlled. For information on the management of adverse events, see Section 13.3.

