8.1.5.4 Follow-up Visits

Subjects who discontinue trial treatment for a reason other than disease progression will move into the Follow-Up Phase and should be assessed every 8 weeks (56 ± 7 days) by radiologic imaging to monitor disease status. Every effort should be made to collect information regarding disease status until the start of new anti-neoplastic therapy, disease progression, death, end of the study or if the subject begins retreatment with pembrolizumab as detailed in Section 8.1.5.2.1. Information regarding post-study anti-neoplastic treatment will be collected if new treatment is initiated.

Subjects who are eligible to receive retreatment with pembrolizumab according to the criteria in Section 8.1.5.2.1 will continue follow-up as scheduled, but data will be recorded separately under a Second Treatment Course Section.

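### The plan does not say whether weeks or cycles fix the scan date, marks no scan at discontinuation and restarts imaging 8 weeks after it, so a planned 9-week gap can reach about 17 weeks

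*Combined protocol and SAP*

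**What the plan says.** **On treatment.** Section 8.1.2.6 states: "CT scans or comparable transactional imaging will be obtained every 9 weeks (=3 treatment cycles". The imaging row of the flow chart (7.1) is labelled "Tumor Imaging (every 9 weeks = 3 cycles" and is marked at main screening, Cycle 4, Cycle 7 and the follow-up visits. It has no mark under Discontinuation or the 30-day safety visit. A footnote gives "Treatment cycle length = 21 days".

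**When dosing slips.** The dose-modification table in 6.2.1.2 says of restarting after non-hematological toxicity: "May increase the dosing interval by 1 week for each occurrence". It lists as a ground for discontinuation: "Toxicity does not resolve within 12 weeks of last infusion". Section 8.1.1.9 contemplates longer gaps: "Interruptions from the protocol specified treatment plan for greater than 12 weeks between MK-3475/pembrolizumab doses due to toxicity require consultation".

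**After treatment.** The flow chart schedules follow-up visits "Every 8 weeks post D/C". Section 8.1.5.4 says that patients who stop for a reason other than progression "should be assessed every 8 weeks (56 ± 7 days) by radiologic imaging to monitor disease status". Under 8.1.1.6.3, new anti-cancer therapy moves the patient to survival follow-up, where no imaging is marked.

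**Analysis.** Section 9.5 defines PFS as running from enrollment to progression or death, and duration of response from response to progression or death. It gives no rule for missed scans or new therapy. Section 6.11 counts every treated patient as evaluable.

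**The concern.** Radiographic progression can be dated no earlier than the scan that shows it. If the time between scans depends on whether a patient has been delayed, held or stopped, so does the recorded progression date. The error goes one way: patients with toxicity or early stops appear to progress later, and PFS and duration of response look longer.

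There is a second effect, on response. A patient who stops before the Cycle 4 scan and starts another therapy before the first follow-up scan may never be assessed after baseline, yet stays in the denominator. Part A is decided by 3 responses in 35, so it matters that the plan says how such a patient is counted.

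**Working it through.** **Inputs.** Cycle of 21 days and scans every 9 weeks or 3 cycles (7.1, 8.1.2.6); interval lengthened by 1 week per occurrence and a 12-week limit from the last infusion (6.2.1.2); follow-up imaging at 56 ± 7 days (8.1.5.4), counted from D/C (7.1); baseline scan between day −28 and day −1 (7.1).

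**1. The plan's own figure.** 3 × 21 days = 63 days = 9 weeks. It reproduces when no cycle is delayed.

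**2. A stop without progression just before a due scan.** The gap is the time since the last scan plus the wait after D/C: 9 + 8 = 17 weeks, or 16 to 18 with the ± 7-day window. Example: scan at week 9, D/C just before week 18, next scan at week 26; 26 − 9 = 17. This does not depend on whether weeks or cycles govern. It needs only the missing D/C scan and the restarted clock, counted from formal D/C.

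**3. Stops before the first on-study scan.** With D/C 3 weeks after dose 1, 2 or 3, the first scan falls at week 3 + 8 = 11, 6 + 8 = 14 or 9 + 8 = 17 from first dose. From a day −28 baseline scan, add 4: 15, 18 or 21 weeks.

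**4. Only if scans follow delayed cycles.**
- 4-week cycles: 3 × 4 = 12 weeks.
- A 12-week dose gap, then resumption: the three dosing intervals between scans total 12 + 3 + 3 = 18 weeks.
- A 12-week hold ending in D/C: (last scan to last dose) + 12 + 8. After the first, second or third dose of a scan block this is 0 + 12 + 8 = 20, 3 + 12 + 8 = 23 or 6 + 12 + 8 = 26 weeks. Example of the last: scan at week 9, last dose at week 15, D/C at week 27, next scan at week 35; 35 − 9 = 26.

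**5. Effect on PFS (illustration only).** The share of affected patients is not in the documents, so I assumed 10% or 30%. I also assumed exponential PFS with a true median of 17 or 25 weeks, last dose equally likely at weeks 0, 3, …, 24, all progression radiographic and no unscheduled scans. Against a fixed 9-week schedule:

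| Affected patients | Rise in mean detection time, all patients | Rise in detected median |
|---|---|---|
| Stop 3 weeks after last dose | about 0.05 to 0.22 week | 0 to 2 weeks |
| Full 12-week hold, then D/C, 10% affected | about 0.3 to 0.4 week | 0 to 2 weeks |
| Full 12-week hold, then D/C, 30% affected | about 0.9 to 1.1 weeks | 5 to 8 weeks |

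The medians jump because scans fall on a coarse grid. The hold rows also need the cycle reading.

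**6. Effect on response (illustration only).** An unscanned patient cannot be recorded as a responder but stays in the denominator, so the observed rate can only fall. Part A power, P(X ≥ 3 | n = 35, p = 0.12), is 0.808, matching the stated 80%. If 5, 10 or 20% of responses were missed (assumed), p becomes 0.114, 0.108 or 0.096 and power 0.778, 0.744 or 0.666.

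**The case against.** **The text says weeks.** Section 8.1.2.6 gives 9 weeks first, and the bracket may only translate it for a 21-day cycle. No section says that a scan moves when a dose moves. This stands: on a calendar reading the 12-, 18- and 20- to 26-week gaps in step 4 disappear. But the flow chart puts the marks in cycle columns, so the other reading is open too, and nothing settles it.

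**D/C may mean last dose.** The flow chart puts the safety visit 30 days after D/C, while 8.1.5.3.1 puts it about 30 days after the last dose. If the two are the same date, a patient last dosed at week 15 is scanned at week 23, 14 weeks after the week-9 scan. In the hold example week 23 has passed by the time treatment is stopped at week 27, so a scan is due at once, after 27 − 9 = 18 weeks. This too stands, which is why the figures of 17 and 26 are tied to formal D/C. Even so, 14 weeks exceeds the planned 9.

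**There are safeguards.** Section 8.1 allows unscheduled procedures, 8.1.4.1 asks for final-visit activities at discontinuation, and 8.1.5.4 asks for every effort to collect disease status. The first is discretionary, the second does not reach imaging because none is marked in that column, and the third sets no scan date. Several severe immune-related events require permanent discontinuation under 6.2.1.2, so those patients do not follow the long-hold path.

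**Stronger inferences to resist.** A reader might infer that anyone with a toxicity delay or early stop goes 16 to 26 weeks unscanned. The figures do not support that: 4-week cycles give 12 weeks, and a stop 3 weeks after dose 1 gives a scan at week 11 from first dose. A reader might also infer a between-arm bias or a false success on the primary endpoint. There is one arm, PFS is secondary and untested, and an unscanned patient can only count against the drug.

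**Conclusion.** The point holds as a gap in the assessment schedule that is worth closing. Counting from formal D/C, a stop without progression just before a due scan leaves about 17 weeks (16 to 18) between scans, nearly twice the planned 9, whichever unit governs on treatment. The 12-week gap holds only if scans follow delayed cycles. The 26-week gap is a worst case: it also needs a full 12-week hold after the third dose of a scan block, D/C dated at the end of the hold, and no unscheduled scan.

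Observed PFS and duration of response are lengthened in the affected patients. How much cannot be derived from the documents, because they give no rate of holds or early stops. The same is true of any loss of response data, whose direction is conservative.

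**What to change.** In 8.1.2.6, 8.1.5.4 and the flow chart:

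- Schedule imaging every 9 calendar weeks from Cycle 1 Day 1 (± 7 days), irrespective of dose holds or lengthened intervals, and delete the equation with 3 cycles.
- Keep the same clock after discontinuation until progression or new therapy, in place of every 8 weeks from D/C.
- State that a patient with no post-baseline scan counts as a non-responder. The calendar clock cannot recover a patient who starts new therapy before week 9, so this sentence is needed as well.

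The planned gap between on-study scans is then 9 weeks, and at most 9 + 1 + 1 = 11 if one scan is a week early and the next a week late.

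The cost is wording. Scan numbers stay about the same: some scans come earlier in delayed patients, and there are slightly fewer after D/C. The downside is that some scans fall away from dosing visits. No dosing or stopping rule changes.
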